16.1 Study Leadership

The scientific leadership for the study and oversight of sites participating in the study is provided by the RECOVER Clinical Science Core (CSC) at the NYU Grossman School of Medicine. The RECOVER CSC collaborates with the RECOVER DRC for data management and data storage at the RECOVER biorepository at Mayo Clinic for biospecimen storage. The activity of the RECOVER Cores is overseen by a Steering Committee composed of the Core Pls, NIH Scientific Program leads, and Chairs of RECOVER Consortium study committees, an Executive Committee composed of NIH Institute leadership and Centers for Disease Control leadership, and an OSBM composed of experts in longitudinal observation studies, epidemiology, bioethics, and biostatistics. The Steering Committee, Executive Committee and OSMB will meet at a minimum of twice yearly.

17 Conflict of Interest Policy

All recipient institutions and investigators in the PASC consortium will comply with the requirements of 42 CFR 50, Subpart F, "Responsibility of Applicants for Promoting Objectivity in Research for which PHS Funding is Sought" (FCOI Regulation), as implemented in the 2011 Final Rule for grants and cooperative agreements.

The requirements promote objectivity in research by establishing standards that provide a reasonable expectation that the design, conduct, or reporting of research funded under PHS grants or cooperative agreements will be free from bias resulting from any conflicting financial interest of an investigator. An

"investigator" is someone defined as the PD/PI and any other person, regardless of title or position who is responsible for the design, conduct, or reporting of research funded by PHS, or proposed for such funding which may include, for example, collaborators or consultants.

Each Institution shall maintain an up-to-date, written, enforced policy on financial conflicts of interest that complies with the regulation and make the policy available via a publicly accessible Web site.

These FCOI requirements do not apply to Federal employees or Federal agencies. Federal agencies have their own set of rules governing financial conflicts of interest for employees.

When submitting a grant application, the signature of the Authorized Organization Representative (AOR) will certify each PASC Consortium applicant institution's compliance with the requirements of 42 CFR 50, Subpart F, including that:

19.1 Appendix 1: Schedule of assessments

	Time After Index Date																
eCRF	Baseline	3m	6m	9m	12m	15m	18m	21m	24m	27m	30m	33m	36m	39m	42m	45m	48m
Enrollment	A																
Tier 1-2 Consent	Α																
Identity	Α																
Visit	Α	Α	Α	Α	Α	Α	Α	Α	Α	Α	Α	Α	Α	Α	Α	Α	Α
Comorbidities	В	В	В	В	В	В	В	В	В	В	В	В	В	В	В	В	В
COVID Treatment*	В																
Medications	В																
Change in Medications		В	В	В	В	В	В	В	В	В	В	В	В	В	В	В	В
Demographics	С																
PASC Symptoms	С	С	С	С	С	С	С	С	С	С	С	С	С	С	С	С	С
Vaccine	С	С	С	С	С	С	С	С	С	С	С	С	С	С	С	С	С
SDoH	С																
SDoH Follow-Up		С	С	С	С	С	С	С	С	С	С	С	С	С	С	С	С
Alcohol/Tobacco	С																
Alcohol/Tobacco Follow-Up		С	С	С	С	С	С	С	С	С	С	С	С	С	С	С	С
Disability	С																
Pregnancy	С																
Pregnancy Follow-Up		С	С	С	С	С	С	С	С	С	С	С	С	С	С	С	С
Tier 1 Office Visit	Α		Α		Α				Α				Α				Α
Biospecimens	Α	Α	Α		Α				Α				Α				Α
Lab Results	Α	Α	Α		Α				Α				Α				Α
Tier 2/Tier 3 Tests	Α	Α	Α	Α	Α	Α	Α	Α	Α	Α	Α	Α	Α	Α	Α	Α	Α

Legend

- **A** Completed by research coordinator
- **B** Completed by research coordinator with review/validation by participant
- **C** Completed by participant
- * COVID Treatment not collected on uninfected controls.

The 39-48m schedule will be repeated for subjects who are more than 48 months after infection while the study is still ongoing.

19.2 Appendix 2: Tier 1 topics, tests and procedures (see CRFs for specific questions and data fields)

All Tier 1 questions, tests and procedures may be done using home visits.

All Tier 1 questions, tests and procedures may be done in pregnant populations. This includes the 30 second sit-to-stand, active standing test and capnography procedures which are no more than minimal risk. As the 30 second sit-to-stand and active standing test procedures involve sitting and standing for brief periods of time while blood pressure is taken, it does not pose a risk to pregnant individuals.

Category	Element	Interval
Demographics	Name and contact information (retained locally)	At enrollment and every 3 months thereafter
Demographics	Alternate contacts (retained locally)	At enrollment and every 3 months thereafter
Demographics	Date of birth	Once, on enrollment
Demographics	Race and ethnicity	Once, on enrollment
Demographics	Biological sex	Once, on enrollment
Demographics	Gender identity	Once, on enrollment
Demographics	Sexual orientation	Once, on enrollment
Demographics	Marital status	At enrollment and every 3 months thereafter
Social determinants	Education	Once, on enrollment
Social determinants	Number of people in household	Once, on enrollment
Social determinants	Homelessness	At enrollment and every 3 months thereafter
Social determinants	Description of living place	At enrollment
Social determinants	Community cohesion	Once, on enrollment
Social determinants	Primary language	Once, on enrollment
Social determinants	Fluency in English	Once, on enrollment
Social determinants	Birthplace	Once, on enrollment
Social determinants	Financial insecurity	At enrollment and every 3 months thereafter
Social determinants	Employment	At enrollment and every 3 months thereafter
Social determinants	Income in 2019	Once, on enrollment
Social determinants	Access to health care	Once, on enrollment
Social determinants	Health insurance	At enrollment and every 3 months thereafter
Social determinants	Loss of insurance because of COVID pandemic	Once, on enrollment
Social determinants	Hunger Vital Sign	Once, on enrollment
Social determinants	Discrimination	Once, on enrollment
Social determinants	Social support	Once, on enrollment
Social determinants	Alcohol and substance use	At enrollment and every 3 months thereafter
Baseline disability	Baseline disability	Once, on enrollment

Category	Element	Interval
Acute COVID	Diagnosis method	Once, on enrollment
Acute COVID	Site and level of care for initial infection	Once, on enrollment
Acute COVID	Treatments received for initial infection	Once, on enrollment
Long COVID	Participation in Long COVID Treatment Trial(s)	At enrollment and every 3 months thereafter
Pregnancy	Pregnancy status	At enrollment and every 3 months thereafter
Pregnancy	Pregnancy outcomes	At enrollment and every 3 months thereafter where relevant
Vaccination	Vaccination status and vaccine details	At enrollment and every 3 months thereafter
Comorbidity	Immunocompromised condition and specific types	At enrollment and every 3 months thereafter
Comorbidity	Rheumatologic, autoimmune or connective tissue disease and specific types	At enrollment and every 3 months thereafter
Comorbidity	Diabetes and specific type	At enrollment and every 3 months thereafter
Comorbidity	Gastrointestinal, liver, or kidney disease and specific type	At enrollment and every 3 months thereafter
Comorbidity	Active cancer or cancer treatment and specific type	At enrollment and every 3 months thereafter
Comorbidity	Dementia or cognitive impairment and specific type	At enrollment and every 3 months thereafter
Comorbidity	Central nervous system infection, inflammatory disease or demyelinating disease and specific type	At enrollment and every 3 months thereafter
Comorbidity	Seizure disorder	At enrollment and every 3 months thereafter
Comorbidity	Neuromuscular disease and specific type	At enrollment and every 3 months thereafter
Comorbidity	Movement disorder and specific type	At enrollment and every 3 months thereafter
Comorbidity	Cardiovascular disease and specific type	At enrollment and every 3 months thereafter
Comorbidity	Stroke or bleed and specific type	At enrollment and every 3 months thereafter
Comorbidity	Asthma	At enrollment and every 3 months thereafter
Comorbidity	Chronic obstructive pulmonary disease	At enrollment and every 3 months thereafter
Comorbidity	Other chronic lung disease	At enrollment and every 3 months thereafter
Comorbidity	Use of oxygen at home	At enrollment and every 3 months thereafter

Category	Element	Interval
Comorbidity	Anxiety, depression or PTSD	At enrollment and every 3 months thereafter
Comorbidity	Schizophrenia or bipolar disorder	At enrollment and every 3 months thereafter
Comorbidity	Other mental health disorder	At enrollment and every 3 months thereafter
Comorbidity	Sickle cell anemia	At enrollment and every 3 months thereafter
Comorbidity	Chronic pain syndrome or fibromyalgia	At enrollment and every 3 months thereafter
Comorbidity	Myalgic encephalomyelitis/chronic fatigue syndrome	At enrollment and every 3 months thereafter
Comorbidity	POTS or other form of dysautonomia or autonomic dysfunction and specific type	At enrollment and every 3 months thereafter
Comorbidity	Obesity	At enrollment and every 3 months thereafter
Comorbidity	Gynecologic problems	At enrollment and every 3 months thereafter
Comorbidity	Thyroid problems	At enrollment and every 3 months thereafter
Comorbidity	Blood or blood clotting problems	At enrollment and every 3 months thereafter
Comorbidity	Transplant and type	At enrollment and every 3 months thereafter
Comorbidity	Headache problems	At enrollment and every 3 months thereafter
Comorbidity	Sleep problems	At enrollment and every 3 months thereafter
Comorbidity	Allergy problems	At enrollment and every 3 months thereafter
Comorbidity	Infections	At enrollment and every 3 months thereafter
Comorbidity	Other health problems	At enrollment and every 3 months thereafter
Medications	Complete medication list	At enrollment and every 3 months thereafter
Symptoms	Overall health status	At enrollment and every 3 months thereafter
Symptoms	Social function	At enrollment and every 3 months thereafter
Symptoms	Physical function	At enrollment and every 3 months thereafter
Symptoms	Fatigue and fatigue details	At enrollment and every 3 months thereafter
Symptoms	Post-exertional malaise (e.g., feeling exhausted after walking)	At enrollment and every 3 months thereafter

Category	Element	Interval
Symptoms	Weakness in limbs	At enrollment and every 3 months thereafter
Symptoms	Fever, chills, sweats or flushing	At enrollment and every 3 months thereafter
Symptoms	Loss of or change in smell or taste	At enrollment and every 3 months thereafter
Symptoms	Pain in any part of body and site of pain	At enrollment and every 3 months thereafter
Symptoms	Headache details	At enrollment and every 3 months thereafter
Symptoms	Chest pain details	At enrollment and every 3 months thereafter
Symptoms	Shortness of breath or trouble breathing and details	At enrollment and every 3 months thereafter
Symptoms	Cough	At enrollment and every 3 months thereafter
Symptoms	Change in voice	At enrollment and every 3 months thereafter
Symptoms	Palpitations, racing heart, arrhythmia, skipped beats	At enrollment and every 3 months thereafter
Symptoms	Swelling of lower legs and details	At enrollment and every 3 months thereafter
Symptoms	Gastrointestinal symptoms and details	At enrollment and every 3 months thereafter
Symptoms	Bladder problems and details	At enrollment and every 3 months thereafter
Symptoms	Nerve problems and details	At enrollment and every 3 months thereafter
Symptoms	Problems with anxiety, depression, stress, or trauma-related symptoms like nightmares or grief	At enrollment and every 3 months thereafter
Symptoms	Depression screen and assessment	At enrollment and every 3 months thereafter
Symptoms	Suicidality screen and assessment	At enrollment and every 3 months thereafter
Symptoms	Anxiety screen and assessment	At enrollment and every 3 months thereafter
Symptoms	Stress	At enrollment and every 3 months thereafter
Symptoms	Problems thinking or concentrating and details	At enrollment and every 3 months thereafter
Symptoms	Problems with sleep and details	At enrollment and every 3 months thereafter
Symptoms	Faint, dizzy, "goofy," difficulty thinking soon after standing up from a sitting or lying position and details	At enrollment and every 3 months thereafter
Symptoms	Color changes in your skin, such as red, white or purple and details	At enrollment and every 3 months thereafter

Category	Element	Interval
Symptoms	Skin rash	At enrollment and every 3 months thereafter
Symptoms	Changes in sweating	At enrollment and every 3 months thereafter
Symptoms	Excessively dry eyes	At enrollment and every 3 months thereafter
Symptoms	Excessively dry mouth	At enrollment and every 3 months thereafter
Symptoms	Excessive thirst	At enrollment and every 3 months thereafter
Symptoms	Vision problems (blurry, light sensitivity, difficulty reading or focusing, floaters, flashing lights, "snow") and details	At enrollment and every 3 months thereafter
Symptoms	Problems with hearing (hearing loss, ringing in ears) and details	At enrollment and every 3 months thereafter
Symptoms	Hair loss	At enrollment and every 3 months thereafter
Symptoms	Problems with teeth or gums	At enrollment and every 3 months thereafter
Symptoms	Change in menstruation or menopause and details	At enrollment and every 3 months thereafter
Symptoms	Changes in desire for, comfort with or capacity for sex	At enrollment and every 3 months thereafter
Change in symptoms since infection	Changes in symptoms reported before and after index date	Once, at second visit or most recent visit if implemented after
Post-COVID utilization	Hospitalization since COVID or last assessment	At enrollment and every 3 months thereafter
Post-COVID utilization	Emergency department visit since COVID or last assessment	At enrollment and every 3 months thereafter
Clinical assessment	Height, weight, BMI	0, 6 months after infection then yearly
Clinical assessment	Waist circumference (cm)	0, 6 months after infection then yearly
Clinical assessment	Seated vital signs (blood pressure, heart rate, respiratory rate, oxygen saturation)	0, 6 months after infection then yearly
Clinical assessment	30 second sit to stand	0, 6 months after infection then yearly
Clinical assessment	Active standing test	0, 6 months after infection then yearly
Clinical assessment	Capnography	0, 6 months after infection then yearly
Clinical assessment	Wearable with continuous remote monitoring for ECG, RR, SpO2, sleep fragmentation, actigraphy	Continuous

Category	Element	Interval
Laboratory study	Comprehensive metabolic panel with cystatin-C	0, 3, 6 months after infection then yearly if abnormal
Laboratory study	Complete blood count with differential	0, 3, 6 months after infection then yearly if abnormal
Laboratory study	Lipid panel	0, 3, 6 months after infection then yearly if abnormal
Laboratory study	Hemoglobin A1c	0, 3, 6 months after infection then yearly
Laboratory study	Coagulation panel	0, 3, 6 months after infection then yearly if abnormal
Laboratory study	D-dimer	0, 3, 6 months after infection then yearly if abnormal
Laboratory study	Troponin	0, 3, 6 months after infection then yearly if abnormal
Laboratory study	NT-pro BNP	0, 3, 6 months after infection then yearly if abnormal
Laboratory study	Thyroid panel	0, 3, 6 months after infection then yearly if abnormal
Laboratory study	25-hydroxy vitamin D	0, 3, 6 months after infection then yearly if abnormal
Laboratory study	Urinalysis	0, 3, 6 months after infection then yearly if abnormal
Laboratory study	Urine microalbumin and creatinine	0, 3, 6 months after infection then yearly if abnormal
Laboratory study	hsCRP	0, 3, 6 months after infection then yearly if abnormal
Laboratory study	SARS-CoV-2 spike and/or nucleocapsid antibody	On enrollment for uninfected controls
Laboratory study	SARS-CoV-2 NAAT	On enrollment for uninfected controls
Laboratory study	SARS-CoV-2 spike and nucleocapsid antibodies	Once
Laboratory study	T-cell reactivity assays	Once

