6.1 Study Design

[figure not shown]
This is an ambi-directional longitudinal meta-cohort study (combined retrospective and prospective) to determine the clinical spectrum, progression, prevalence, and incidence of PASC (COVID-19). Individuals with and without COVID-19 infection will be enrolled at varying stages during and after first infection (Figure 1).

We will include subjects who meet our inclusion and none of the exclusion criteria and analyze the core set of questions on demographics, comorbidity, COVID-19 vaccination status, acute COVID-19 clinical course, current clinical condition/symptom, and outcomes as tiered testing. Participants who consent and contribute data to the study will count towards target enrollment numbers.

Figure 1: Enrollment plan for people with infection

Adult recruitment cohorts

[figure not shown]

Many of the participating health centers utilize electronic health record (EHR) systems. This facilitates the pooling of data to ask and answer numerous research questions applicable to the care of subjects with or at risk for COVID-19. Data will be entered into the secure HIPAA compliant REDCap database for analysis and storage.

A subset of participants will be asked to undergo Tier 2 (**Appendix 3**: Tier 2 questions, tests and procedures) and in some cases Tier 3 testing (**Appendix 4**: Tier 3 tests and procedures), if available at the local study site. In order to meet the sample size targets described in Section 12.2 below, participants are organized into four "buckets" based on their COVID-19 infection status and whether or not they present with relevant PASC symptoms. To ensure statistical power to differentiate between each protocol-specified bucket for analysis, this protocol specifically assigns Tier 2 and Tier 3 assessments to participants in each bucket. These assessments are assigned to the appropriate number of infected participants (Bucket 1) and uninfected participants (Bucket 2) who have these relevant symptoms. Then, they are assigned to participants without symptoms by randomly selecting the appropriate number of infected (Bucket 3) and uninfected (Bucket 4) participants. This process is shown in **Table 2**.

Table 2: Distribution of Participants by COVID-19 Infection History and Relevant Symptoms

	Infected subject	Uninfected subject
With relevant symptom(s)	[Bucket 1]	[Bucket 2]
Without relevant symptom(s)	[Bucket 3]	[Bucket 4]

[figure not shown]

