8.1 Overview of Study Schedule

Data will be collected at baseline and then following the study schedule, which starts at time of first infection for those enrolled during first infection or after their first infection without an active infection at time of enrollment; at time of reinfection if enrolled during an acute infection; or at time of negative COVID-19 test, for those who are uninfected. Uninfected pregnant individuals will begin the study schedule on their delivery date. See **Table 3**. Collection will be tiered such that all enrolled patients will undergo Tier 1 data collection, and those with abnormal findings on Tier 1 collection may progress to more intensive, invasive, or costly Tier 2 and Tier 3 data collection. We anticipate that approximately 30% of participants will undergo each Tier 2 test and a maximum of 20% of enrollees will undergo each Tier 3 test for any given symptom, including both those with relevant symptoms and a random sample of 5.6% of SARS-CoV-2 infected and 11.4% of uninfected subjects without relevant symptoms. All patients will undergo at least one in-person visit annually, which can be provided at home if provisions are made for home blood and biospecimen collection.

Table 3: Index date and study schedule date, by enrollment type

Enrollment Category	Index Date	Study Schedule Start Date	
Acute Infected (First Infection)	First positive SARS-CoV-2 test	First positive SARS-CoV-2 test	
	result date or, if test not	result date or, if test not	

	available, date of COVID symptom onset	available, date of COVID symptom onset
Acute Infected (Reinfected)	First positive SARS-CoV-2 test result date or, if test not available, date of COVID symptom onset	Most recent positive SARS- CoV-2 test result date or, if test not available, date of COVID symptom onset
Acute Uninfected	Qualifying negative SARS-CoV-2 test result date	Qualifying negative SARS-CoV-2 test result date
Post-Acute Infected	First positive SARS-CoV-2 test result date or, if test not available, date of COVID symptom onset	First positive SARS-CoV-2 test result date or, if test not available, date of COVID symptom onset
Post-Acute Uninfected	Qualifying negative SARS-CoV-2 test result date. For pregnancy sites only , index date is the prior delivery date	Qualifying negative SARS-CoV-2 test result date. For pregnancy sites only , index date is the prior delivery date

Home Visits

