8.2 Baseline/Enrollment Visit

A core set of questions on demographics, habits, social determinants of health, comorbidity, medications, SARS-CoV-2 vaccination status, acute SARS-CoV-2 clinical course and current clinical condition/symptom inventory will be answered by the patient upon enrollment. Following completion of the core questions, a minimal physical examination will be performed, including collection of height, weight, vital signs (including orthostatic vital signs) and measurement of waist circumference. Additional clinical examinations will be performed at that time as indicated by patient responses to the symptom questionnaires. This visit will also include collection of blood, urine, saliva, tears, and stool both for initial clinical testing and banking (see below), and/or retrieval of specimens already banked for the patient during acute COVID. If enrollment occurs at time of acute COVID-19 and the patient is too ill to participate in the complete baseline assessment or assessment is not safe for research personnel, some patient-reported elements may be deferred until recovery but should then be completed as close to the acute infection as possible. Should a patient lose capacity to consent or participate in research during the study, all research activities will be paused. Research activities will only resume once a member of the clinical team caring for the patient deems the patient capable of consent or participation. See Appendix 1: Schedule of assessments for schedule of assessments. The study schedule resets for participants who were enrolled as uninfected and then sustain an on-study infection, such that the new index date will be the date of first infection. The corresponding "enrollment" date for this new index date is the first visit date following the new infection.

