12.1 Hypotheses to be Tested

The following hypotheses will be addressed in the analytic approach to Aim 1:

- Hypothesis 1a: Clinically meaningful PASC cases and sub-phenotypes will be discernable based on a combination of candidate PASC symptoms, and potentially other clinical features.
- Hypothesis 1b: Cumulative incidence of long-term sequelae differs between SARS-CoV-2 infected and uninfected individuals, overall and stratified by hospitalization.
- Hypothesis 1c: Incidence rate of long-term sequelae differs between SARS-CoV-2 infected and uninfected individuals, overall and stratified by hospitalization
- Hypothesis 1d: The point prevalence of long-term sequelae differs between SARS-CoV-2 infected and uninfected individuals, overall and stratified by hospitalization.
- Hypothesis 1e: The severity of long-term sequelae differs between SARS-CoV-2 infected and uninfected individuals, overall and stratified by hospitalization.

The following hypotheses will be addressed in the analytic approach to Aim 2:

- Hypothesis 2a: The risk of PASC among infected individuals will vary by: demographic and clinical characteristics, vaccine status at the time of infection, severity of disease (including hospitalization and admittance to ICU), drug exposures, pregnancy during acute infection and calendar time.
- Hypothesis 2b: The rate of recovery from PASC among individuals with PASC will vary by: (i)
 demographic and clinical characteristics and vaccine status at the time of infection, and (ii) severity
 of disease (including hospitalization and admittance to ICU), drug exposures, and pregnancy during
 acute infection.

The following hypotheses will be addressed in the analytic approach to Aim 3:

- Hypothesis 3a: PASC and PASC sub-phenotypes will be associated with concurrent and subsequent abnormal laboratory results and other clinical and subclinical features.
- Hypothesis 3b: The association between PASC and PASC sub-phenotypes with concurrent and subsequent abnormal laboratory results and other clinical and sub-clinical features will be modified by demographic factors, including sex, age and race/ethnicity.
- Hypothesis 3c: Recovery from PASC will be associated with laboratory results and other clinical and subclinical features.
- Hypothesis 3d: The association between SARS-CoV-2 infection and PASC and PASC subphenotypes will be mediated by abnormal laboratory results and other clinical and sub-clinical features.

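### Level of care and treatment for a first infection are recorded once, at enrollment, so participants enrolled mid-illness may have the record closed before their care ends

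*Protocol*

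**What the plan says.** **What is collected, and when.** Section 19.2 (Appendix 2), under Acute COVID, lists "Site and level of care for initial infection" and "Treatments received for initial infection". Both have an interval of once, at enrollment. In Section 19.1 (Appendix 1) the COVID Treatment form is marked at Baseline only, completed by the coordinator with participant review. Its footnote reads "COVID Treatment not collected on uninfected controls". In the same table Medications, social determinants, alcohol/tobacco and pregnancy each have a follow-up row. COVID Treatment has none.

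**Who is enrolled.** Section 6.1: "Individuals with and without COVID-19 infection will be enrolled at varying stages during and after first infection". Table 3 in Section 8.1 makes acute first infection a formal enrollment category.

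**What happens at baseline.** Section 8.2 has the core questions, including "acute SARS-CoV-2 clinical course and current clinical condition/symptom inventory will be answered by the patient upon enrollment". If an acutely ill patient is too sick, or assessment is unsafe for staff, "some patient-reported elements may be deferred until recovery but should then be completed as close to the acute infection as possible".

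**What uses the data.** Hypothesis 2a in Section 12.1 lets PASC risk vary by "severity of disease (including hospitalization and admittance to ICU), drug exposures, pregnancy during acute infection and calendar time". Hypothesis 2b does the same for recovery, again naming severity with ICU admission and drug exposures.

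**The concern.** For someone enrolled after the illness, a single record at enrollment looks back over a finished episode. For someone enrolled in the first days of a first infection, the same form describes an episode still under way. If that person is later given an antiviral, admitted or moved to intensive care, the entry can stay at untreated and outpatient.

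The variable would then mean care up to enrollment in one group and all care for the infection in the other. A pooled estimate of the effect of ICU care or a drug on PASC would partly reflect when people enrolled. An analysis plan can adjust for enrollment type, but it cannot supply care that was never recorded.

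Acute-care data may matter operationally too. Appendix 5 uses mechanical ventilation during acute COVID to oversample for several tests, although the protocol does not say which field supplies that trigger.

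**Working it through.** No stated figure decides this point, so the main check is a comparison of provisions.

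**Step 1. Can the form be completed before care ends?** Yes. Enrollment during a first infection is allowed (6.1, Table 3), the form is due at Baseline (Appendix 1), and the acute course is asked at enrollment (8.2). The exception in 8.2 covers only people too ill or unsafe to assess, and only some patient-reported elements. It does not reach a person who completes baseline and then worsens.

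**Step 2. Does another provision update the record?**

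| Provision | Can recover | Not stated |
|---|---|---|
| Hospitalization and emergency visits, every 3 months (Appendix 2) | Later admission, yes/no | ICU or highest level of care |
| Medication list every 3 months; Change in Medications form | Drugs still in use at a visit, possibly others | In-hospital drugs, or courses finished between visits |
| Acute-infection details from subjects or the EHR (Section 1); hospitalization history and treatment among central data (9.6) | Possibly all | Timing, or that they override the baseline entry |
| Consent for EHR and claims linkage (13.3) | Possibly all | Any rule for updating the form |

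What remains is ICU or highest level of care, and short acute drug courses.

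**Step 3. Who is affected?**
- First-acute enrollees fit enough for baseline: yes.
- Post-acute enrollees: normally no, as the episode is past.
- Crossovers: 8.2 resets enrollment to the first visit after infection. The gap recurs only if that visit falls in the acute window.
- Acute reinfected enrollees: no, for the initial infection. It is already past, and Table 3 keeps it as the index date.

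**Step 4. Scale, under assumptions.** The protocol text gives no share of acute enrollees (the enrollment figure is not reproduced), so only a range can be shown. Inputs from Table 7, risk-factor row: prevalence q = 20%, risk with the factor 30%, detectable difference 3.90 points. The risk without it is 30 − 3.9 = 26.1%. With 12,200 infected, the groups are 2,440 and 9,760. The row's 3.90% and 7.60% reproduce as 3.90% and 7.59% at two-sided alpha 0.01 with 90% power. Neither value is stated there.

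Let f be the share of infected participants enrolled acutely and g the share of truly exposed acute enrollees whose exposure the form misses. The overall missed share is m = f × g, taking the exposure to be equally common in both groups. With no false positives and misses unrelated to outcome:

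observed difference = 3.90 × (1 − q) / (1 − q + q·m) = 3.12 / (0.80 + 0.20·m)

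| Assumed f × g | m | Observed difference | Power (alpha 0.01) |
|---|---|---|---|
| 10% × 50%, or 20% × 25% | 5% | 3.12/0.81 = 3.85 | 0.88 |
| 20% × 50%, or 40% × 25% | 10% | 3.12/0.82 = 3.80 | 0.85 |
| 40% × 50% | 20% | 3.12/0.84 = 3.71 | 0.79 |

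The estimate moves little. Power falls more, because the recorded exposed group shrinks. No comparable figure can be given for ICU care, since the protocol states no ICU share. The 25% hospitalized target in 6.2 describes the whole population and concerns the variable that is largely recoverable.

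**The case against.** The strongest reply is that the protocol has several routes to the missing information: utilization and medication items every 3 months, EHR collection of acute-infection details, linkage, and deferral for the sickest. Appendix 2 is also a topic list that points to the CRFs for the fields. The hospitalization item may ask about ICU on a form not shown here. This stands against any claim that the data are lost. It does not answer the narrower point: the schedule fixes one time for these two items, and nothing says a later source corrects them.

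A reader might infer more than the documents support:

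- *That acute enrollees are misclassified as a group.* Some will have finished care by baseline, some are deferred, and some may be corrected from the EHR. The text supports only that they may be.
- *That Hypotheses 1b to 1e are undermined.* They stratify by hospitalization, which the utilization item and EHR largely recover.
- *That reinfected enrollees are recorded too early.* Their schedule starts "at time of reinfection if enrolled during an acute infection", but the items ask about the initial infection, which is over.
- *That a missed share of 20% to 50% can be applied to the full-sample 3.9%.* That treats every infected participant as an acute enrollee.

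**Conclusion.** The point holds in a limited form. The stated timing lets the COVID Treatment record close before care ends for people enrolled in a first acute infection who can complete baseline, and for crossovers first seen in the acute window. The exposed items are ICU or highest level of care and short drug courses. ICU admission and drug exposures are named in Hypotheses 2a and 2b.

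The size is unknown. It depends on the share of acute enrollees and the timing of their care, neither of which is given, and any attenuation is confined to that share. The figures above are illustrative and assume that misses are unrelated to outcome. If those who escalate after enrollment differ in PASC risk from others with the same exposure, the bias need not follow them. It also remains possible that unseen CRFs or EHR rules close part of the gap. The change is worth making because it is cheap and later adjustment cannot replace it.

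**What to change.** In Appendices 1 and 2, have the COVID Treatment form (site, highest level of care, all treatments for that infection) completed or updated once at the 3-month visit, or at the next visit if that is later. Apply this to participants enrolled during a first acute infection, and to crossovers whose first post-infection visit falls in the acute window. State that the updated record defines severity and drug exposure in the analysis.

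Appendix 2 has a precedent: the change-in-symptoms item is taken once at the second visit, or at the most recent visit if introduced later. The same rule would reach people already enrolled.

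The cost is a few minutes of coordinator time. The 3-month visit already has coordinator-completed forms and biospecimen collection. With visits at 90 days ± 45, it falls 90 − 45 = 45 to 90 + 45 = 135 days after the schedule starts, when most acute care should be over.
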